Cover page

Title: Neuromodulation Using Vagus Nerve Stimulation Following Ischemic Stroke as

Therapeutic Adjunct (NUVISTA)

NCT number: NCT05390580, Approval Date: 2/4/2025

Study Title: Vagus Nerve Stimulation following a Large Vessel Occlusion Acute Ischemic Stroke

(NUVISTA)

Principal Investigator: [name] MD

Co-investigator(s): [name] [name]; [name] MD

Sponsor or funding source: None

Objectives

To quantify inflammatory markers in the blood of patients who present with ischemic strokes due to large vessel occlusions to Barnes Jewish Hospital, and determine if treatment with auricular transcutaneous vagal nerve stimulation alters the levels of inflammatory markers in these patients over time, and we will explore if it impacts their overall outcome.

Methods and Measures

Design

This is a randomized open-label, with blinded outcome pilot study to evaluate the effect on inflammatory laboratory values and explore clinical outcomes in patients who present with ischemic strokes due to large vessel occlusions and are treated with either current accepted management, or accepted management in addition to transcutaneous auricular vagal nerve stimulation.

Setting

Patients in this study will be inpatient at Barnes Jewish Hospital

Data Collection Criteria

Adult patients who present with acute ischemic strokes due to large vessel occlusions to Barnes Jewish Hospital will be considered for enrollment in this study. Exclusion criteria will include patients <18 years old, patients with presumed chronic large vessel occlusions, posterior circulation LVOs, NIHSS<6, CTP Penumbra <1/3 total ischemic area, pre-morbid modified Rankin score (mRS) >2, unable to initiate treatment under 36 hours from symptom discovery, life expectancy <3 months, patients' undergoing active cancer or immunosuppressive/modulating therapy, or patients with sustained bradycardia on arrival with a heart rate <50 beats per minute.

Sample size

We anticipate enrolling approximately 80 patients into the study, with random assortment to treatment with standard medical care, and standard medical care with transcutaneous auricular vagal nerve stimulation.

Intervention

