Patients enrolled in the trial will be randomized to treatment with or without electrical stimulation via an auricular, transcutaneous vagus nerve stimulator. All patients will be fitted with the device, we will attach adhesive contacts to the left ear. Stimulation sessions will occur for 20 minutes twice daily during the inpatient period. Patients assigned to the controls arm will have no electricity applied,

those treated with stimulation will be treated with the following parameters: frequency 20 Hz, pulse width 250 μ m, and varying intensities from 0.4 mA to 2 mA (intensity is always titrated to be a level below painful threshold in a patient). The amplitude of stimulation may be reduced if a patient complains of discomfort at the site of stimulation. The site of stimulation will be inspected daily before and after treatment to ensure there is no redness or irritation at the site.

Outcome Measure(s)

The primary endpoints of the study will be changes in the levels of inflammatory markers that include IL-1b, IL-6, TNF-α, and white blood cell count in the blood, as well as specific inflammatory cell counts (neutrophil to lymphocyte ratio, for example) at time of admission, and every day throughout the hospitalization. The secondary exploratory endpoints will be clinical outcomes assessed via the change in daily NIHSS and mRS at 30 and 90 days, as well as safety endpoints with regards to blood pressure and heart rate. We will also do mononuclear cell genetic testing to attempt to identify phenotypes that respond to the intervention. Follow up data will be obtained via chart review, we will obtain the mRS data at 30 days over the phone, and we will make additional outpatient follow up appointments for the research study in order to collect the NIHSS and mRS data at 90 days.

Analytical Plan

Results will be analyzed initially using descriptive statistics. Comparison between groups will be done using chi square tests for proportions, and t-tests or ANOVA procedures for continuous variables. Regression analysis will be performed to identify independent outcome predictors. Other inferential statistical analysis will be conducted as appropriate. Please see document with statistical plan that is attached.

Human Subjects Protection

Subject Recruitment Methods

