day) in each of the two treatment groups and to formally test whether these rates were different. For 30-day NIHSS changes (vs. baseline) and 90-day mRS changes, we used the parallel model, with actual assessment days scaled to standardize the evaluation period to 30 or 90 days, respectively. We characterized the daily change in each WBC or cytokine outcome using a similar model expanded to include the quadratic terms. Treatment-time interactions were tested using likelihood ratio tests comparing models with and without interaction term (NIHSS, mRS) or terms (cytokines, WBC), with significance at two-sided α =0.05. These analyses were adjusted for baseline covariates, including baseline NIHSS (except in NIHSS models, which included this observation), time from LKN to thrombus removal time or recanalization attempt (groin puncture time), and percent reperfusion (0-100%) based on TICI score to obtain a single semicontinuous measure. In sensitivity analyses, we also performed the analysis with a dichotomized TICI scale (reperfused ≥2B, not reperfused <2B) or restricted data to the first five days post-LKN (when most stimulations and hospitalizations had ended). Finally, we explored whether any difference in longitudinal patterns between taVNS and sham depended any of the a priori adjustment variables, i.e., whether any time-treatment interaction depended on one of these three variables. We conducted post-hoc t-tests to compare cytokine levels between groups on each day.

Statistical analysis of safety and exploratory analysis of the Stroke Complications and Poor Outcomes in relation to treatment.

To assess our dichotomous safety endpoints, we used logistic regression models constructed to assess differences in bradycardia, hypotension, infection, hemicraniectomy, hemorrhagic transformation, and deaths amongst treated vs non-treated patients. To explore the hypothesis that taVNS reduces the incidence of complications and poor outcomes, we performed logistic

regression models for discharge related outcomes, defined as: readmission, length of stay, and hospital poor disposition (i.e. nursing home, long-term acute care hospital, or death).

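### Age, known for every patient, is not among the named adjustment covariates, which forgoes a modest gain in precision for the exploratory clinical outcomes

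*Combined protocol and SAP*

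**What the plan says.** In the Expanded Statistical Analysis, the subsection on rate of change covers cytokines, WBC, in-hospital NIHSS, 30-day NIHSS change and 90-day mRS change. It states: "These analyses were adjusted for baseline covariates, including baseline NIHSS". The other two covariates are time from LKN to thrombus removal or groin puncture, and percent reperfusion derived from the TICI score. Baseline NIHSS is dropped as a covariate from the NIHSS models because it is already one of their outcome records. The word for inclusion leaves the list open, but the same paragraph later calls these the a priori adjustment variables and asks "whether any time-treatment interaction depended on one of these three variables". That closes it at three.

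For NIHSS and mRS the tested quantity is the treatment-by-time interaction, by likelihood ratio test, "with significance at two-sided α =0.05".

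The following subsection, on safety and exploratory outcomes, uses logistic regression for safety events and for discharge outcomes, including poor disposition. It lists no covariates. The opening Statistical analysis paragraph says multivariable regression was used except for rare secondary outcomes and adverse effects.

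Age appears only as an eligibility limit under Data Collection Criteria: "Exclusion criteria will include patients <18 years old". The Intervention section says "Patients enrolled in the trial will be randomized to treatment with or without electrical stimulation" and describes no stratification. Outcome Measure(s) makes the inflammatory markers primary and the clinical outcomes secondary and exploratory.

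**The concern.** Age is a plausible predictor of disability, discharge destination and death after a large stroke. It is fixed before randomisation and available for everyone. Adjusting for a prognostic baseline variable usually sharpens a treatment comparison, and it removes the part of the estimate's error that comes from the arms differing on that variable. With about 80 patients and no stratification described, a visible age gap between the arms could easily occur.

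The NIHSS models are the thinnest. Once baseline NIHSS is dropped as a covariate, the two that remain both describe the recanalisation procedure, and neither is a patient characteristic.

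What is at stake is the precision of the secondary exploratory clinical comparisons. There is also a matter of credibility: adding age only after an imbalance has been seen would be a data-driven choice.

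**Working it through.** **Inputs from the documents.** Total sample: "We anticipate enrolling approximately 80 patients into the study" (Sample size). Two-sided alpha 0.05. The plan states no power, effect size, SD or allocation ratio, so there is no figure of its own to reproduce.

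**Assumptions.** 40 patients per arm; age SD 14 years; the strength of the age-outcome association, shown as a range.

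**1. Comparison at a single time.** With 40 per arm, the effect detectable with 80% power without age is (1.960 + 0.842) × √(2/40) = 0.626 SD. If age has partial correlation r with the outcome given the other covariates, the residual SD is multiplied by √(1 − r²). The unadjusted trial with the same power has 80/(1 − r²) patients.

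| r | Power with age | Equivalent unadjusted N |
|---|---|---|
| 0.1 | 80.4% | 81 |
| 0.2 | 81.6% | 83 |
| 0.3 | 83.6% | 88 |
| 0.4 | 86.4% | 95 |
| 0.5 | 89.9% | 107 |

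The gain is 0.4 to 9.9 points.

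**2. The planned slope test.** Simulated random-intercept model: 80 patients, 3 to 7 daily records each, intercept SD 1, residual SD 0.6, linear time, likelihood ratio test of treatment-by-time, 1,000 runs per setting, true effect 0.06 SD per day.
- Age correlated 0.3 with the intercept: power 34.3% without age, 34.6% with an age main effect.
- Age correlated 0.5 with the intercept: 34.6% and 34.5%.

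Simulation error is about 1.5 points (√(0.345 × 0.655/1000) = 0.015), so there is no gain. An effect of age that is constant over time largely cancels out of a slope.

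If age also alters the slope (assumed 0.05 SD per day), rejection with no treatment effect was 7.1% without age, 6.5% with a main effect and 5.6% with age-by-time (error about 0.7 to 0.8 points). With the true effect present, the figures were 35.4%, 35.2% and 31.8%. In this setting the age-by-time term moves the error rate towards 5%; it does not raise raw power.

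**3. The 90-day mRS change.** If the parallel model amounts to one change per patient, the interaction test compares change scores, and age-by-time acts as covariate adjustment of the change. Simulated with 40 per arm and 6,000 runs, power without and with age was 80% and 81%, 79% and 83%, 78% and 85%, 79% and 89% for an assumed age-change correlation of 0.2, 0.3, 0.4 and 0.5. Null error stayed near 5%. This agrees with step 1.

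**4. Logistic model for a common outcome.** Assumed: 80 patients, outcome near 50%, treatment log-OR −1.2 (OR exp(−1.2) = 0.30), the three named covariates already in the model. Two simulations were run with different assumed effects for those covariates. The first (3,000 runs) had null error 5 to 6.5%. The second (5,000 runs) used critical values corrected to 5%.

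| Age log-OR per SD | First: without, with age | Second: without, with age |
|---|---|---|
| 0.3 | not run | 63.2%, 62.3% |
| 0.5 | 65%, 67% | 63.9%, 64.3% |
| 0.7 | 62%, 65% | 58.2%, 60.2% |
| 0.9 | 58%, 64% | 55.5%, 60.4% |

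The gain is about 0 to 6 points.

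**5. Chance imbalance.** The SE of the standardised age difference is √(2/40) = 0.224, so its 95% range is ±0.44 SD. A gap of 5 years or more has probability 2 × P(Z > 5/(14 × 0.224)) = 2 × P(Z > 1.60) = 0.11. At an age log-OR of 0.7 per SD, a 5-year gap moves the treatment log-OR by 0.7 × 5/14 = 0.25, a factor of exp(0.25) = 1.28 on the odds ratio. The treatment estimate's standard deviation in the step 4 setting is about 0.54, so the shift is 0.25/0.54 = 0.46 of a standard error.

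**The case against.** Four stronger readings are tempting, and the documents support none of them.

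- **The clinical comparisons in general lose power.** For the NIHSS and mRS slope tests an age main effect changes nothing measurable. Age matters there only if it affects the slope or the change score, and then only through an age-by-time term.
- **Age was left out of a fixed set in the logistic models.** The three-variable set belongs to the longitudinal models. The discharge and safety models list no covariates, so the gap there is non-specification. The step 4 assumption that the three covariates carry over is not in the text.
- **An age gap biases the treatment estimate.** Under randomisation a chance gap is ordinary imprecision, already covered by the test's error rate. The illustrative gap has an 11% chance and moves the estimate by less than half a standard error.
- **The trial's main conclusion is at risk.** The primary endpoints are inflammatory markers, and nothing here shows an effect on them.

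It is also fair to say that age's strength as a predictor, given NIHSS and reperfusion, appears nowhere in the documents, and that at a weak association (log-OR 0.3) the logistic gain vanishes. The SAP is written in the past tense, so age added now could be a post-hoc covariate. The general promise in the Analytical Plan of a regression for outcome predictors does not answer the point, since it names neither age nor an adjusted treatment comparison.

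These arguments limit the size of the point. They do not remove it: age is available, is not named in any treatment comparison, and costs almost nothing to include.

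**Conclusion.** The point holds in a limited form. The longitudinal adjustment set omits age, and the discharge models name no covariates. For secondary exploratory outcomes this gives up a modest amount of precision: about 0 to 6 power points in a logistic model for a common outcome, about 0.4 to 10 points in a single-time or change-score comparison, and none in the slope tests from a main effect alone.

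All these figures rest on 40 per arm and on assumed age associations; the logistic figures also assume a treatment odds ratio of 0.30. The change-score figure further assumes that the 90-day mRS model reduces to one change per patient. It is a worthwhile improvement, not a flaw that undermines the trial.

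**What to change.** In the SAP:
- Add continuous age at randomisation and its interaction with time to the NIHSS and mRS longitudinal models. The interaction is what reaches the tested slope.
- State the covariates of each logistic model, and include continuous age as a main effect for non-rare outcomes such as poor disposition.
- Leave rare safety events unadjusted, as the opening Statistical analysis paragraph already implies.

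If the analyses have already been run, keep the planned models and report the age-adjusted ones as a labelled sensitivity analysis.

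No new data are needed. The cost is one extra parameter in each logistic model and two in each NIHSS or mRS model, in about 80 patients, with little or no return if age proves weakly prognostic.

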Statistical analyses were performed using Stata/MP version 18 (StataCorp LLC 2023, Statistical Software, College Station, TX) and Python packages Scipy and Statsmodels. All continuous variables were retained as continuous, except where noted. Multivariable regression was used to examine treatment group associations with outcomes, except for rare secondary outcomes/adverse effects. Following FDA recommendations, an intention-to-treat (ITT) approach was implemented. Primary ITT analyses were conducted without transformation of continuous outcome variables because ≥35 observations were available.

Statistical analysis of rate of change in cytokines, WBC, and neurological outcomes in taVNS vs. sham treatment.

Longitudinal data were analyzed using mixed effects models per the FDA, with person as a random effect, given multiple records per person. For cytokine models, assay plate was included as an additional random effect. This approach accommodated irregularly timed points, less restrictive missing data assumptions, and time-varying variables. To complement our primary ITT approach, treatment also was handled as time-varying when noted, with assignment occurring at randomization. All longitudinal models included treatment, time since LKN, and their interaction term(s) as primary independent variables to test whether the pattern of change over time differed between the taVNS and sham groups. Time was modeled quadratically for cytokine and WBC outcomes to capture the known U-shaped associations with time when modeling these outcomes and linearly for in-hospital NIHSS scores based on panel data plots. For NIHSS, a single model was constructed to estimate the rate of change (change in NIHSS per

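### The post-hoc daily t-tests on cytokines compare only patients still in hospital; day-specific contrasts should come from the SAP's own mixed model

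*Combined protocol and SAP*

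**What the plan says.** The protocol's Outcome Measure(s) section has the inflammatory markers measured "at time of admission, and every day throughout the hospitalization". It describes no blood draw after discharge. mRS is taken by telephone at 30 days, and the later research visit is arranged "in order to collect the NIHSS and mRS data at 90 days".

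The formal comparison is in Expanded Statistical Analysis, under the heading on rate of change in cytokines, WBC and neurological outcomes: "Longitudinal data were analyzed using mixed effects models per the FDA, with person as a random effect". For cytokines, "For cytokine models, assay plate was included as an additional random effect". Time since LKN enters quadratically. The covariates are baseline NIHSS, time from LKN to thrombus removal or attempt, and percent reperfusion. The treatment-by-time terms are tested by likelihood ratio "with significance at two-sided α =0.05". One reason given for the model is: "This approach accommodated irregularly timed points, less restrictive missing data assumptions, and time-varying variables".

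A sensitivity analysis of these models "restricted data to the first five days post-LKN (when most stimulations and hospitalizations had ended").

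The section then closes with: "We conducted post-hoc t-tests to compare cytokine levels between groups on each day". It states no last day, adjustment or handling of patients who have been discharged or have died.

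**The concern.** A t-test on a given day can use only patients sampled that day. Once discharges begin, those are no longer the randomised groups. Leaving hospital happens after randomisation and plausibly tracks recovery. Under its safety and exploratory heading, the SAP itself examines length of stay, disposition and death as outcomes that stimulation might improve. If patients with lower inflammation leave sooner and stimulation lowers inflammation, the stimulated patients still being sampled are weighted towards those who responded least.

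The mixed model uses each patient's earlier samples, so it can allow for discharge that depends on them. A separate t-test per day cannot. As stated, it also leaves out the plate effect and the three covariates.

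Inflammatory markers are the primary endpoints, and the interaction test says only whether the trajectories differ. A reader who wants to know when they differ may well turn to the daily tests. On later days those could understate a real effect.

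**Working it through.** The documents give no marker SD, effect size, discharge rate or power calculation, so there is no stated figure to reproduce. Total N of about 80 comes from the Sample size section. The allocation ratio is not stated, and 40 per arm is assumed. All effects below are in SD units, shown as the size of the reduction, and every discharge input is an assumption.

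**1. Loss of numbers alone.** If most of 80 patients have left after day 5, fewer than about 20 per arm remain. The detectable difference at 80% power and two-sided 0.05 is (1.960 + 0.842) × √(2/n). For n = 20 this is 2.802 × 0.316 = 0.89.

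| n per arm | Detectable difference | Power for 0.63 SD |
|---|---|---|
| 40 | 0.63 | 80% |
| 20 | 0.89 | 51% |
| 12 | 1.14 | 34% |
| 8 | 1.40 | 24% |

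**2. Daily t-tests when discharge may depend on the marker.** Simulation with 2,000 runs per row:
- Person SD 0.8 and residual SD 0.6, so total SD = √(0.64 + 0.36) = 1.
- The true reduction reaches 0.63 by day 3 and stays there.
- The log-odds of discharge after each day's sample are a daily base minus γ × marker. The base is −3, −2.2, −1.5 and −1.2 on days 1 to 4, then −1.

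| Link (γ) | Mean n on day 5, stimulated / control | Difference shown, day 5 / 7 | Power, day 5 / 7 |
|---|---|---|---|
| None (0) | 21.6 / 21.6 | 0.63 / 0.63 | 52% / 29% |
| Moderate (1) | 14.3 / 19.9 | 0.52 / 0.46 | 33% / 15% |
| Strong (2) | 10.5 / 17.7 | 0.41 / 0.33 | 21% / 11% |
| Reversed, high markers leave first (−1) | 25.1 / 19.8 | 0.54 / 0.49 | 46% / 28% |

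With γ = 0, 15.7 of 40 (39%) remain on day 6, which fits the SAP's remark that most stays had ended. With no true effect and the same discharge rule in both arms, rejection stayed at 4–6%.

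**3. A second set-up, with stimulation also changing discharge.** SD 1, 60% of variance between patients, discharge possible from day 2 with hazard 0.25 × HR^arm × exp(−c × marker). The ranges cover repeat runs and two readings of the hazard (as a rate or as a daily probability).

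| True effect | HR | c | Day-5 difference shown by t-test |
|---|---|---|---|
| 0.50 | 1 | 0 | 0.50 |
| 0.50 | 1 | 0.3 | 0.46 |
| 0.50 | 1 | 0.8 | 0.31 to 0.40 |
| 0.50 | 1.5 | 0.8 | 0.14 to 0.28 |
| 0 | 2 | 0 | about 0 |
| 0 | 1.3 | 0.8 | stimulated 0.10 worse |
| 0 | 2 | 0.8 | stimulated 0.20 to 0.33 worse |

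A day-by-arm generalised least squares fit to the same kind of data, with the true covariance, gave 0.48 to 0.52 where the truth was 0.50, and 0.01 where it was 0.

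**4. The proposed replacement.** A mixed model with quadratic time by arm and a person intercept, but no plate effect or covariates, was fitted to simulated data with discharge driven by observed values (250 runs per row). The true difference was 0.63 × (t/4 − t²/64), so on day 5 it was 0.63 × (1.25 − 0.391) = 0.541.

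| Day 3 / 5 / 7 | γ = 1 | γ = 2 |
|---|---|---|
| Truth | 0.384 / 0.541 / 0.620 | 0.384 / 0.541 / 0.620 |
| Raw daily difference | 0.383 / 0.479 / 0.509 | 0.315 / 0.402 / 0.354 |
| Model contrast | 0.393 / 0.551 / 0.631 | 0.384 / 0.543 / 0.627 |

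The model contrast removes the dilution. The true curve here was quadratic, so this does not test a wrong time shape.

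**The case against.** The best defence is that these tests carry little weight. They take one sentence, are labelled post-hoc, and have no alpha level or decision attached. The arm comparison is the adjusted mixed model, chosen partly for its handling of missing data and backed by a five-day sensitivity analysis. This stands, and it limits the point to the supplementary daily results.

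It is also fair that the bias is conditional. With no link between marker and discharge there is none, and with a weak link it is small (0.46 for 0.50). Nor is the power advantage of a model mainly a measure of discharge bias. In the second set-up at HR 1, day-5 power was 37–39% for the model and 21% for the t-test with selection. Without selection it was 40% against 28%, a gap that comes from borrowing information across days.

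Three stronger readings are tempting, and the documents do not support them:
- A reader might infer that the SAP compares the arms by daily t-tests, so that its main result is biased. It does not; the formal test is the likelihood ratio test.
- A reader might infer that stimulation will look pro-inflammatory. That needs marker-driven discharge and a strong effect of stimulation on discharge together. Even at HR 2, rejection was only about 11% in the run that reported it.
- A reader might infer that the t-tests certainly run past day 5. The SAP sets no limit, but does not say that they do. The five-day restriction is listed for the longitudinal models and is not extended to the t-tests.

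The label post-hoc does not settle the matter. It lowers the weight of the daily results without making them comparisons of the randomised groups.

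**Conclusion.** The concern holds for the supplementary daily t-tests on cytokines, and for those only. On later days they condition on still being in hospital, a state that stimulation may alter, and as stated they lack the main model's random effects and covariates.

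Loss of power as patients leave is certain. Bias depends on a link between marker and discharge that the documents do not quantify. With a clear link, a true 0.50 SD effect shows as roughly 0.3 to 0.4 SD on day 5, and lower if stimulation speeds discharge. These sizes rest on assumed SDs, correlations, discharge rates and equal allocation; the direction was the same in both set-ups.

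The main treatment-by-time test does not share this flaw when discharge depends on observed values. Neither it nor the contrasts derived from it repair discharge or death driven by values that were never observed.

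**What to change.** Replace the sentence on daily t-tests. For day t since LKN, estimate the arm difference from the adjusted cytokine model already specified, as β(treatment) + β(treatment × time) × t + β(treatment × time²) × t², with its confidence interval. Keep the person and plate random effects and the same covariates. A model with day as a category by arm can serve as an optional check on the quadratic shape. It should not be the main version, because continuous time suits the irregular sampling times.

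Suggested wording:

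> Day-specific differences between arms in each cytokine are estimated as linear combinations of the treatment and treatment-by-time coefficients of the adjusted mixed model, with 95% confidence intervals, and are post-hoc. The number of patients sampled per arm is reported for each day. No between-arm test is made on days when fewer than half of the randomised patients in either arm are still being sampled.

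The change needs SAP wording and a short post-estimation step on data already collected, with no new patients or samples. In return, the daily contrasts rely on the model's time shape and on discharge depending on observed values, and sparse late days get no test.

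### The post-hoc daily cytokine t-tests leave out each patient's admission level, so the day-specific contrasts are less precise than the collected data allow

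*Combined protocol and SAP*

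**What the plan says.** The Outcome Measure(s) section states: "The primary endpoints of the study will be changes in the levels of inflammatory markers". Sampling is set "at time of admission, and every day throughout the hospitalization". Every patient should therefore have an admission value for each cytokine.

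The Expanded Statistical Analysis makes a mixed model its main longitudinal analysis: "Longitudinal data were analyzed using mixed effects models per the FDA, with person as a random effect, given multiple records per person". Assay plate is a further random effect for cytokines. The model contains treatment, time since LKN (quadratic for cytokines) and their interactions, "to test whether the pattern of change over time differed between the taVNS and sham groups". The interaction is assessed by a likelihood ratio test "with significance at two-sided α =0.05". The listed adjustment variables are baseline NIHSS, the interval from LKN to the recanalisation procedure, and percent reperfusion.

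The same section ends with one further sentence on cytokines: "We conducted post-hoc t-tests to compare cytokine levels between groups on each day". It gives no admission term, change score, covariate or significance level for these tests.

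**The concern.** The endpoint is a change, but the daily tests examine a level. A plain two-sample t-test takes no covariate, so the admission value, usually a good predictor of a later value in the same patient, goes unused. That leaves avoidable noise in each contrast.

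The interaction test is a single joint test of whether the curves differ. The daily tests are the only day-specific arm comparison of cytokines that the plan names, so a statement about the day on which taVNS lowered a cytokine would most naturally rest on them. The same patients reappear from day to day. If the arms happen to differ at admission, part of that difference shows up in several consecutive tests, where it could pass for a sustained effect or mask one. This applies even on the first days, before discharges thin the sample.

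**Working it through.** **No stated figure to reproduce.** The documents give no power, effect size, SD or sample-size derivation.

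**Inputs from the documents.** About 80 patients (Sample size); admission and daily samples (Outcome Measure(s)); two-sided 0.05, stated for the interaction tests only.

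**Assumptions.** Equal allocation, so n = 40 per arm (the ratio is not stated); 0.05 two-sided for the t-tests too; SD = 1 at admission and on day d; roughly normal data; correlation ρ between admission and day-d levels of 0.3, 0.5 or 0.7.

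**Step 1: power.** The standard error of a difference in levels is √(2/40) = 0.224 SD. The effect giving the t-test 80% power is (1.960 + 0.842) × 0.224 = 0.626 SD. Adjusting for the admission level multiplies the residual SD by √(1 − ρ²), so the standardised effect becomes 0.626/√(1 − ρ²).

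| ρ | √(1 − ρ²) | Effective effect | Power, adjusted | Gain over 80% |
|---|---|---|---|---|
| 0.3 | 0.954 | 0.657 | 83.6% | 3.6 points |
| 0.5 | 0.866 | 0.723 | 89.9% | 9.9 points |
| 0.7 | 0.714 | 0.877 | 97.5% | 17.5 points |

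Simulation (20,000 trials per setting) gave 78% to 79% for the t-test and 81.8%, 88.7% and 97.2% for the adjusted test. With 20 per arm the gains are the same if the effect is again set for 80% power (0.886 SD).

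The gain depends on the starting power as well as on ρ. At 40 per arm with an effect of 0.3 SD (26.8% starting power) it is 2.2, 7.2 and 19.9 points. With 0.8 SD (94.7%) it is 1.6, 3.8 and 5.2 points.

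**Step 2: carry-over of an admission imbalance.** The 95% range for a chance admission difference is ±1.96 × 0.224 = ±0.44 SD. Given an imbalance D and no treatment effect, the day-d difference has mean ρD and SD 0.224 × √(1 − ρ²). The t-test rejects beyond 1.991 × 0.224 = 0.445 SD (78 degrees of freedom). With D = 0.44:

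| ρ | Carried over (ρD) | SD | False-positive rate, t-test |
|---|---|---|---|
| 0.3 | 0.132 | 0.213 | 7.4% |
| 0.5 | 0.220 | 0.194 | 12.3% |
| 0.7 | 0.308 | 0.160 | 19.5% |

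Using 1.96 in place of 1.991 gives 7.9%, 13.0% and 20.7%. In simulation the adjusted test stays at about 5% under the same imbalance. At a typical imbalance of 0.22 SD the t-test's rate is 5% or lower (5.0%, 4.7% and 3.8% by the 1.96 calculation). Over all randomisations its simulated error is 5.1% to 5.3%.

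**Step 3: several days together.** I simulated five post-admission days with equal correlation between all days, no effect and the same 0.44 SD imbalance. Two or more daily t-tests were falsely significant in about 7% to 8%, 16% and 27% of trials at ρ = 0.3, 0.5 and 0.7. With adjustment the figure was 3% to 4%.

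**Step 4: change scores are not the remedy.** A t-test on change from admission has SD √(2(1 − ρ)). For the 0.626 SD effect its power is 65.8%, 80.0% and 95.1% at ρ = 0.3, 0.5 and 0.7. That is a loss below 0.5, no gain at 0.5, and less than the adjusted test throughout.

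**The case against.** The strongest reply is that the plan already deals with change where it matters. The mixed model treats patients "with person as a random effect, given multiple records per person", tests the pattern of change, and can absorb a constant difference between arms in its treatment term. It also yields each arm's fitted trajectory. The daily tests are labelled post-hoc, and no decision rule rests on them. All of this stands. It limits the point to a supporting analysis, but does not supply an adjusted day-specific contrast.

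Three stronger readings are tempting, and the documents do not support them.

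- **The tests lose about 10 points of power.** That figure requires ρ near 0.5 and 80% starting power, and neither is in the documents. A constant ρ over days is also uncertain, since the plan expects a U-shaped course.
- **The tests are invalid because the data are paired.** taVNS and sham patients are different people, so an independent-samples comparison between arms is correct in a parallel-group trial. What is missing is covariate adjustment.
- **Any admission imbalance is repeated in full each day.** Only the fraction ρ carries over, and the inflated error rates apply only given a large imbalance, about 1 in 20 at 0.44 SD.

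It is also fair to say that the wording could include the admission day among those tested, in which case readers could see an imbalance. Seeing it would not remove it from the later comparisons.

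**Conclusion.** The point holds as a cheap improvement to a post-hoc analysis. The daily tests are valid, but they ignore an available covariate that is closely tied to the endpoint's definition. Under the stated assumptions, adjustment adds about 4 to 17 points to 80% starting power, and it removes a conditional false-positive rate of about 7% to 20% when admission levels differ by 0.44 SD. These sizes rest on an assumed correlation, equal allocation, equal SDs and approximate normality. The last is uncertain for cytokines: "Primary ITT analyses were conducted without transformation of continuous outcome variables", and the plan does not say what scale the t-tests use. Nothing here calls the main mixed-model test into question.

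**What to change.** Replace the t-test sentence with wording such as: *As a post-hoc analysis, for each day after admission (days defined by time since LKN, as in the longitudinal models), the level of each cytokine was compared between groups by linear regression on treatment group and the same patient's admission level of that cytokine; the adjusted difference is reported with its 95% confidence interval.* Equivalent baseline-adjusted contrasts from the mixed model would serve as well, and would keep assay plate and the plan's adjustment variables. Do not test the admission day as an outcome.

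No new samples are needed. A patient without an admission sample needs a simple baseline imputation, for example the overall mean, to stay in the comparison. The section is written in the past tense, so any daily tests already run would have to be repeated. The change does not address the number of days and cytokines examined, which is a further reason to keep the post-hoc label.
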